11.11 INDEPENDENT REVIEWER (IR)

An Independent Reviewer, from the site in Korea, will be utilized in this clinical trial in order to

reduce the variability between investigators in assessing the CT images (and as needed, MRI and Ultrasound) and to minimize potential bias. The Independent Reviewer will review all CT scans taken throughout the study (including at screening) using the images stored in the hospital's database and without referring to the radiology imaging report in order to avoid influence in the assessment. All images will be taken in accordance with the hospital's Standard of Care. At baseline, the independent reviewer will confirm the presence of one lesion, and its location, size, and BCLC stage.

According to the standard practice at the site in Korea, the independent review will classify the ablation as:

- complete tumor ablation with adequate margin
- complete tumor ablation with insufficient margin
- incomplete tumor ablation.

This assessment will be done for the scans taken following the ablation procedure (Visit 2, for technical success) and at the 1-month visit (Visit 3, for technical efficacy).

At all post-ablation follow up visits, the central reviewer will assess recurrence of the target lesion, progression, meaning a new lesion(s), or lack thereof. If there is a progression or recurrence, the central reviewer will again assess number of lesions, location, size and BCLC stage.

The assessment by the independent reviewer will only be used for the purpose of statistical analysis while the assessment by the investigators will be used for the treatment of the subjects in the study as well as reported in the analysis.

12.0 ASSESSMENT OF SAFETY

12.1 ADVERSE EVENT REPORTING

Adverse Events associated with the device, or the procedure, and incidents such as those specified in local laws and regulations, including Korean Guidelines for GCP⁵³, will be captured and reported during this study. Monitoring of study sites by Sponsor personnel will ensure that adverse events, and product complaints are documented.

12.1.1 Definitions

12.1.1.1 Pre-existing Condition

A pre-existing condition is one that is present at the start of the study, and is to be reported as part of the subject's medical history. It must be reported as a new Adverse Event if the intensity, frequency, or the character of the condition worsens during the study treatment.

To avoid confusing pre-existing conditions with AEs during data analysis, the study sites must make all attempts to provide start dates for all baseline medical conditions. Any pre-existing condition that has worsened in intensity, frequency, or the character of the condition should be recorded on the AE eCRF as an exacerbation of the pre-existing condition and the start date will be recorded as the time when the exacerbation occurred.

12.1.1.2 Adverse Event

An AE is an untoward medical occurrence (sign, symptom or disease) in a patient or clinical trial subject and which does not necessarily have a causal relationship with the study medical device. An untoward medical occurrence includes any new, undesirable medical experience or worsening of a pre-existing condition, which occurs at any point from study treatment to Visit 11.

Note: A local tumor progression by itself should be considered a progression of disease (pre-existing condition). Progression of disease does not meet the definition of an AE.

All reportable AEs must be reported to the Sponsor within 2 weeks of the site becoming aware.

12.1.1.3 Adverse Device Effect (ADE)

An Adverse Device Effect is an adverse event related to the use of a study medical device. This includes any adverse event resulting from insufficient or inadequate Instructions for Use, deployment, implantation, or operation, or any malfunction of the study medical device and also includes any event resulting from use error or from intentional misuse of the study medical device.

ADEs must be reported to the Sponsor within 2 weeks of the site becoming aware.

12.1.1.4 Unexpected Adverse Device Effect

An unexpected ADE is an adverse device effect, the nature or severity of which is not consistent with the applicable product information (e.g. Investigator's Brochure or product labeling).

All unexpected ADEs must be reported to the Sponsor within 72 hours of the site becoming aware.

12.1.1.5 Serious Adverse Event

A Serious Adverse Event (SAE) is any AE that:

- 1) Results in death or is life-threatening,
- 2) Requires inpatient hospitalization or prolongation of hospitalization,
- 3) Results in persistent or significant disability/ incapacity, or
- 4) Results in a congenital anomaly/ birth defect.

Note:

- “Death” should not be reported as an AE. The cause of death should be reported as the AE. The only exception is “Sudden Death” when the cause is unknown.
- Planned hospitalization or procedure for a pre-existing condition, or a procedure required by the study protocol, without serious deterioration in health, is not considered a serious adverse event.

All reportable SAEs must be reported to the Sponsor within 24 hours of the site becoming aware.

12.1.1.6 Serious Adverse Device Effect (SADE)

A serious adverse device effect is an adverse device effect that has resulted in any of the consequences characteristic of a serious adverse event or that might have led to any of these consequences if suitable action had not been taken or intervention had not been made or if circumstances had been less opportune.

All SADEs must be reported to the Sponsor within 24 hours of the site becoming aware.

12.1.1.7 Unexpected Serious Adverse Device Effect (USADE)

Serious adverse device effect which by its nature, incidence, severity or outcome has not been identified in the current version of the risk analysis report.

Note: Expected serious adverse device effect is an effect which by its nature, incidence, severity or outcome has been identified in the IFU and IB.

All USADEs must be reported to the Sponsor within 24 hours of the site becoming aware.

12.1.1.8 Severity of Adverse Events

It is the Investigator’s responsibility to assess the severity of an AE. A change in severity may constitute a new reportable AE.

The following guideline should be used to determine the severity of each adverse event:

- **MILD:** Awareness of experience, but easily tolerated. No medical intervention required.
- **MODERATE:** Enough discomfort to interfere with usual activities. Medical intervention required.
- **SEVERE:** Inability to carry out usual activities. Medical intervention (including

hospitalization or prolongation of hospitalization) required.

12.1.1.9 Relationship/Attribution of Adverse Events

It is the Investigator’s responsibility to assess the relationship of an AE to the study procedure (microwave ablation) and study device(s).

The following guidelines should be used in determining the relationship of an adverse event to the study device, study procedure, or other causality:

- **NOT RELATED:** The event is due to extraneous causes.
- **POSSIBLY RELATED:** The event is unlikely associated, but cannot be ruled out with certainty.
- **PROBABLY RELATED:** The event is likely associated, but another cause cannot be ruled out with certainty.
- **DEFINITELY RELATED:** The event is associated with a high degree of certainty; or
- **UNKNOWN:** The event cannot be defined by the categories listed above.

12.1.1.10 Complications

A major complication is defined as an event that leads to substantial morbidity and disability (e.g., results in the unexpected loss of an organ) that increases the level of care, or results in hospital admission, or substantially lengthens the hospital stay (SIR classifications C–E). This includes any case in which a blood transfusion or interventional drainage procedure is required. All other complications are considered minor. It is important to stress that several complications such as pneumothorax or tumor seeding can be either a major or minor complication depending on severity. For tumor seeding this would depend on whether or not the ectopic tumor focus can be successfully ablated or otherwise treated.

Table 5: SIR Classification System for Complications by Outcome⁵⁴

Minor Complications
 
A. No therapy, no consequence
 
B. Nominal therapy, no consequence; includes overnight admission for observation only.

Major Complications
 
C. Require therapy, minor hospitalization (< 48 hours)
 
D. Require major therapy, unplanned increase in level of care, prolonged hospitalization (> 48 hours)
 
E. Permanent adverse sequelae
 
F. Death.

Complications are differentiated as:

- Immediate complications: Up to 6–24 hours following the procedure
- Peri-procedural complications: Within 30 days, and
- Delayed complications: Greater than 30 days after ablation.

Ablation-related complications should include problems encountered within the peri-procedural (30–day) time period that can be related in any way to the procedure, as well as additional complications that were identified at delayed follow-up imaging

that were judged to be highly likely due to the ablation therapy (biliary ductal stricture, tumor seeding along the needle track, etc.).

12.1.1.11 Reporting Adverse Events

Investigator's Responsibility:

The Investigator is required to report all AEs experienced by the subject from Visit 2B until the subject completes Visit 4 (3 months after the ablation procedure) or withdraws before Visit 4. All AEs during this time period, regardless of their relatedness to the study device(s) or procedure, must be reported in the AE eCRF within 2 weeks after the site becomes aware of the information. The investigator will evaluate the severity of the event, and its relatedness to the study device or procedure. Any necessary medical management of the event will be recorded in the subject's medical record/source document. All AEs must be followed until resolution or until they become stable but ongoing.

Sponsor's Responsibility:

The Sponsor will follow MFDS's guideline to report safety events related to the study medical devices with the timeline which is regulated by law.

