Statistical Methods:	
Categorical variables will be summarized descriptively by frequencies and associated percentages. Continuous variables will be summarized descriptively by number of subjects, mean, standard deviation, median, minimum, and maximum. Confidence intervals will also be provided for procedure-related variables.
 
The number and percentage of subjects achieving Technical Success will be summarized and an exact 95% confidence interval will be estimated. A similar summary will be provided for Primary Technique Efficacy, as well as for the primary and secondary efficacy rates as previously defined.
 
Local tumor progression rates at 1, 3, 6, 9, 12, 18, 24, 30 and 36 months will be estimated using the Kaplan-Meier method and 95% confidence intervals will be provided.
 
The number and percentage of subjects experiencing adverse events (AEs) will be summarized at the preferred term level using the Society of Interventional Radiology (SIR) clinical practice guidelines for event categorization.
 
Two analyses of study data are planned. The first will occur after 30 subjects have completed the 3-month visit and is intended to provide an initial estimate of device effectiveness for Technical Success as well as to summarize the peri-operative out to 3-month post-operative safety

	
profile of subjects undergoing microwave ablation. There are no plans to use the results of the first analysis for the purpose of stopping the study early. The second analysis will occur after all subjects have completed study participation.

--	--

Table 1: Schedule of Events

Visit No. Visit	Visit1: Screening	Visit2A Pre-Ablation	Visit2B Ablation	Visit2C Post-Ablation	Visit3 1 month	Visit4 3 months	Visit5 6 months	Visit6 9 months	Visit7 1 year	Visit8 18 months	Visit9 2 years	Visit10 30 months	Visit11 3 years	USV Unscheduled Visit ⁸
Interval Windows	Within 5 weeks before ablation	-2 to 0 days	Day 0= Ablation of index tumor	0 to 4 days	1 month (+/- 14 days) after ablation	3 months (+/-28days) after ablation	6 months (+/-28 days) after ablation	9 months (+/-28 days) after ablation	12 months (+/-28 days) after ablation	18 months (+/-28 days) after ablation	24 months (+/-28 days) after ablation	30 months (+/-56 days) after ablation	36 months (+/-28 days) after ablation	NA
Study Activity														
Informed Consent	X													
Demographic Information	X													
Medical/Surgical History	X													

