8. Adverse Event and SAEs: Subjects will be assessed for safety from day of ablation through the 3-year follow-up. All AEs and SAEs will be reported from the day of the ablation up to 3 months after the ablation procedure. Expected serious adverse device effects (SADE), unexpected serious adverse device effects (USADE), life-threatening events, or events that result in death, and all SAEs with definite, possible, probable or unknown relationship to the study device or study procedure, will be reported from day of the ablation through the 3-year follow-up.
9. Unscheduled visits are only for those which are procedure, device or disease related.

NOTE:

- Subjects who have recurred at the target lesion or progressed with a new lesion following the first ablation, and are treated with any treatment post progression will be followed every 6 months (+/-28 days) from the day of the first ablation as a clinic visit or, if clinic visit is not possible, a phone contact visit (if a clinic visit is not possible). This will be called a "Reduced Follow-Up Schedule."

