7.2 STUDY ENDPOINTS

Primary:

Technical Success, defined as complete tumor ablation with adequate or insufficient margin, based on contrast-enhanced MRI and CT scans immediately following the ablation procedure.

Secondary:

- Primary Technique Efficacy, defined as complete tumor ablation with adequate or insufficient ablation margin, based on contrast-enhanced MRI and CT scans follow-up at 1 month after the ablation procedure;
- Local tumor progression (LTP) rate, evaluated at 1, 3, 6, 9, 12, 18, 24, 30 and 36 months after the ablation of the index tumor;
- Primary efficacy rate, defined as the percentage of target tumors successfully eradicated following the ablation procedure;
- Secondary efficacy rate, defined as the percentage of tumors that have undergone successful repeat ablation following identification of local tumor progression;
- Progression free survival and overall survival rates at 36 months after the ablation procedure;
- Rate of adverse events reported through 3 months and cumulatively through study completion; Quality of Life, as measured by VAS pain score, EORTC QLQ-C30 and EORTC QLQ-HCC18, before the ablation procedure and at each post-ablation visit;
- Health economics associated with the ablation procedure: complete procedure time, ablation time, no. of ablations, length of stay, no. and types of probes used.

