15.3 INTERVAL WINDOWS

Subjects are scheduled for 9 post-ablation visits under this protocol. For summarization of selected endpoints at post-ablation time points, the following windows will be defined around each scheduled visit to identify the corresponding measurement to be summarized for that visit:

- Visit 3 – 1 month (± 14 days) post ablation;
- Visit 4 – 3 months (± 28 days) post ablation;
- Visit 5 – 6 months (± 28 days) post ablation;
- Visit 6 – 9 months (± 28 days) post ablation;
- Visit 7 – 12 months (± 28 days) post ablation;
- Visit 8 – 18 months (± 28 days) post ablation;
- Visit 9 – 24 months (± 28 days) post ablation;
- Visit 10 – 30 months (± 56 days) post ablation; and
- Visit 11 – 36 months (± 28 days) post ablation.

In cases where multiple measurements fall into a given window, the measurement that is closest in time (number of days) to the scheduled measurement will be utilized in all analyses. Subject and site compliance with the protocol specified visit windows will be monitored throughout the study and the final SAP may be revised to expand the windows as necessary so as not to exclude relevant subject measurements that may be near the existing windows.

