15.8.6 Analysis of Safety

The number and percentage of subjects experiencing adverse events (AEs) will be summarized at the preferred term level using the SIR clinical practice guidelines for event categorization. Summarization of AEs will also be provided by (1) by relationship to study procedure (MWA); (2) by relationship to the device (study devices); and, (3) by maximum severity. Serious AEs will be summarized in a similar manner.

Concomitant procedures and hospital readmission will be summarized with counts and percentages. Summary statistics for laboratory parameters over time may be provided. Post ablation concomitant medications will be listed for all subjects.

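### Full adverse-event reporting ends at Visit 4 in one place and at 3 months in another, and the 3-month AE rate has no onset cut-off

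*Combined protocol and SAP*

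**What the plan says.** Two stop rules for full AE reporting stand side by side.

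- **Visit-based.** Section 12.1.1.11 requires the investigator to "report all AEs experienced by the subject from Visit 2B until the subject completes Visit 4"; the limit in full reads "until the subject completes Visit 4 (3 months after the ablation procedure) or withdraws before Visit 4". Section 12.1.1.12 applies the same limit to SAEs, and Sections 11.7 to 11.10 narrow reporting to the Sponsor once Visit 4 has passed.
- **Time-based.** Table 1 note 8 in the Synopsis says: "All AEs and SAEs will be reported from the day of the ablation up to 3 months after the ablation procedure". It does not mention Visit 4.

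Visit 4 is allowed at "3 months (+/-28days) after ablation" in Table 1 and at "3 months (± 28 days) post ablation" in Section 15.3. Section 15.3 adds that "the final SAP may be revised to expand the windows as necessary". Neither place converts 3 months to days.

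The endpoint in Section 7.2 is "Rate of adverse events reported through 3 months and cumulatively through study completion". For the analysis, Section 15.8.6 says: "The number and percentage of subjects experiencing adverse events (AEs) will be summarized at the preferred term level". It gives no onset cut-off and no adjustment for time observed. Section 15.8.4 makes the safety profile out to 3 months part of the first analysis, which is triggered by 30 subjects completing the visit.

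After Visit 4 a narrower set stays reportable to Visit 11: serious adverse device effects, life-threatening events, deaths, and SAEs whose relationship to device or procedure is definite, probable, possible or unknown.

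**The concern.** The endpoint names a fixed period, but the collection rule follows a visit date that can move by four weeks either way. An early Visit 4 closes full reporting before the named period ends. A late one keeps it open beyond that period, and nothing in the analysis section removes the extra events.

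The two rules can also give the site opposite instructions. Suppose Visit 4 takes place on day 65 and an unrelated, non-serious event starts on day 75. Note 8 makes that event reportable; Section 12.1.1.11 does not.

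At stake is whether the 3-month AE percentage covers the period on its label. Section 15.7 intends an informed comparison with published results, and such a comparison needs a defined period. The first analysis may include only about 30 subjects, so one subject moves the percentage by 1/30, or 3.3 points.

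**Working it through.** The plan gives no figure on this point to reproduce, so the check is of the windows.

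**Inputs.** Visit 4 tolerance of 28 days (Table 1, Section 15.3). Days in 3 months, M: assumed 91, with other values below.

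**End of full reporting under the visit-based rule.** Earliest = M − 28; latest = M + 28; ratio = (M + 28)/(M − 28).

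| M (assumed) | Earliest day | Latest day | Ratio |
|---|---|---|---|
| 90 | 62 | 118 | 1.90 |
| 91 | 63 | 119 | 1.89 |
| 92 | 64 | 120 | 1.88 |
| 84 (12 weeks, extreme) | 56 | 112 | 2.00 |

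**With an onset cut-off at day 91 but collection still ending at Visit 4.** Late attenders are truncated at day 91 and early attenders still stop as soon as day 63. Largest ratio among subjects who complete Visit 4 in window: 91/63 = 1.44.

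**With the cut-off and collection to at least day 91.** Every subject who has not withdrawn is observed for 91 days: ratio 1.00.

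**Effect on the percentage (illustration).** Assume a constant hazard and a true 91-day risk of 30%. Neither assumption comes from the documents. Risk by day d is 1 − 0.7^(d/91).

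- All subjects seen at day 63: 21.9%. All seen at day 119: 37.3%. These are the outer bounds.
- Visit 4 dates spread evenly over days 63 to 119, no cut-off: with k = −ln(0.7)/91 = 0.00392, the mean is 1 − (e^(−63k) − e^(−119k))/(56k) = 29.9%, against 30%.
- Same spread, onset cut-off at day 91, collection still ending at Visit 4: the early half averages 1 − (e^(−63k) − e^(−91k))/(28k) = 26.0% and the late half shows 30%, so the overall figure is (26.0 + 30)/2 = 28.0%.

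For scale, the exact 95% interval for 9 of 30 is 14.7% to 49.4%.

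The second and third results show that the cut-off alone is not enough. Without it, gains from late visits roughly offset losses from early ones. With it, only the losses remain unless collection is also extended.

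**The case against.** The strongest reply is that this is a matter of wording with little numerical effect. Much of that stands.

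- **The rules are meant to be the same.** A reader might infer a flat contradiction. Sections 12.1.1.11 and 12.1.1.12 themselves gloss Visit 4 as 3 months after ablation, so the documents support only two loosely equated rules that diverge inside the visit window.
- **Little that is serious is lost.** A reader might infer that all events after an early Visit 4 disappear. They do not: the serious events listed above remain reportable to Visit 11. Sections 11.7 to 11.10 also have subjects evaluated for all adverse events at later visits; only reporting to the Sponsor narrows. Peri-procedural events (within 30 days) are covered for every subject seen in window.
- **The late side depends on an unstated rule.** Nothing says that events after 3 months will be counted in the rate. Section 15.1 defers detail to an SAP, which could apply an onset cut-off.
- **Delayed complications are not a planned rate.** A reader might compute a wider spread for events after day 30. Section 15.8.6 plans no summary for that class, and the serious related ones continue to Visit 11.
- **Timing may balance out.** The window is symmetric, there is one site, and Section 8.7 has staff contact subjects to keep the schedule. The study has no comparison arm in which collection could differ.

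What does not stand is the idea that the SAP can settle the matter. A cut-off removes late events but cannot supply non-serious events that were not reported between an early Visit 4 and 3 months. Nor can the symmetry argument and the cut-off argument both be used in full, since the cut-off removes the events that produce the balance.

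**Conclusion.** The point holds in a limited form. The visit-based rule and note 8 give different end dates for any subject not seen exactly at 3 months, and the passages need to be reconciled. After an early Visit 4, up to 28 days of non-serious AEs, and of SAEs that are unrelated and neither life-threatening nor fatal, are missing from a rate labelled as running through 3 months. After a late Visit 4, up to 28 days of later events may be included.

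The effect is probably modest. The 1.89 ratio compares two subjects at opposite window limits with no cut-off applied; it falls to 1.44 with one. A reader might take 22% against 37% as the likely distortion. It is not: it compares a cohort seen entirely at the earliest day with one seen entirely at the latest, on an assumed rate and a constant hazard. If AEs cluster soon after the procedure, the distortion is smaller still. A material shift would need systematically early or late visits, for which the documents give no evidence.

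The day figures rest on 3 months being 91 days and on visits inside the present window. Section 15.3 allows the analysis windows to be widened. The endpoint is secondary and descriptive, and the primary endpoint is untouched. The change is still worth making, because events left unreported under the collection rule cannot be recovered at analysis.

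**What to change.** 1. Bring Table 1 note 8, Sections 11.6 to 11.10, and Sections 12.1.1.11 and 12.1.1.12 to one stop rule: report all AEs and SAEs to the later of a defined day (for example day 91) and completion of Visit 4, or to withdrawal if earlier. State the day count for 3 months once.
2. In Section 15.8.6, count in the 3-month rate only AEs with onset on or before that day. Report later events in the cumulative summary.
3. Where Visit 4 was early, cover the remaining days by a short call soon after the defined day, or by a retrospective question at the next visit.

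The cost is protocol and SAP wording, plus an occasional call or question by the site. The drawback is weaker recall of minor events if the question waits for Visit 5. Taking 6 months as 182 days, that window opens at day 154, which is 63 days after day 91 (182 − 28 − 91), so a call is preferable. If collection is left as it is, the cut-off should still be added and the observed time reported beside the rate, but the shortfall for early attenders would remain.
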